18.4 Missing Date of Investigational Product

When the date of the last dose of investigational product is missing for a subject in the Safety Analysis Set, all efforts should be made to obtain the date from the investigator. If it is still missing after all efforts, then the last visit date when investigational product was returned will be used in the calculation of treatment duration.

18.5 Missing Date Information for Prior or Concomitant Medications

For prior or concomitant medications, including rescue medications, incomplete (ie, partially missing) start date and/or stop date will be imputed. When the start date and the stop date are both incomplete for a subject, impute the start date first.

18.6 Incomplete Start Date

The following rules will be applied to impute the missing numerical fields. If the stop date is complete and the imputed start date is after the stop date, then the start date will be imputed using the stop date.

18.6.1 Missing Day and Month

- If the year of the incomplete start date is the same as the year of the date of the first dose of investigational product, then the day and month of the date of the first dose of investigational product will be assigned to the missing fields.
- If the year of the incomplete start date is before the year of the date of the first dose of investigational product, then 31 December will be assigned to the missing fields.
- If the year of the incomplete start date is after the year of the date of the first dose of investigational product, then 01 January will be assigned to the missing fields.

18.6.2 Missing Month Only

- The day will be treated as missing, and both month and day will be replaced according to the above procedure.

18.6.3 Missing Day Only

- If the month and year of the incomplete start date are the same as the month and year of the

date of the first dose of investigational product, then the day of the date of the first dose of investigational product will be assigned to the missing day.

- If either the year is before the year of the date of the first dose of investigational product or if both years are the same but the month is before the month of the date of the first dose of investigational product, then the last day of the month will be assigned to the missing day.
- If either the year is after the year of the date of the first dose of investigational product or if both years are the same but the month is after the month of the date of the first dose of investigational product, then the first day of the month will be assigned to the missing day.

18.7 Incomplete Stop Date

The following rules will be applied to impute the missing numerical fields. If the date of the last dose of investigational product is missing, then replace it with the last visit date. If the imputed stop date is before the start date (imputed or non-imputed start date), then the imputed stop date will be equal to the start date.

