9. PRIOR AND CONCOMITANT MEDICATION

The most updated available version of the World Health Organization drug dictionary will be used to classify prior and concomitant medications by therapeutic class.

Prior medication is defined as any medication with a start date prior to the date of the first dose of investigational product.

Concomitant medication is defined as any medication with a start date prior to the date of the first dose of investigational product and continuing after the first dose of investigational product or with a start date between the dates of the first and last doses of investigational product, inclusive. Any medication with a start date after the date of the last dose of investigational product will not be considered a concomitant medication.

Both prior and concomitant medication usage (including ADHD medication) will be summarized by the number and proportion of subjects within each preferred term for the Safety Analysis Set by treatment group and pooled doses. Medications can be counted both as prior and concomitant medication. Multiple medication usage by a subject in the same category will be counted only once. Both prior and concomitant ADHD medication usage (based on indication), excluding investigational product, will also be summarized by the number and proportion of subjects within each preferred term for the Safety Analysis Set by treatment group and pooled doses.

All prior and concomitant medication will be listed for the Safety Analysis Set. Separate listings will also be provided for prior and concomitant ADHD medication and prior and concomitant ADHD behavioral therapy.

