18.7.3 Missing Day Only

- If the month and year of the incomplete stop date are the same as the month and year of the date of the last dose of investigational product, then the day of the date of the last dose of investigational product will be assigned to the missing day.
- If either the year is before the year of the date of the last dose of investigational product or if both years are the same but the month is before the month of the date of the last dose of investigational product, then the last day of the month will be assigned to the missing day.
- If either the year is after the year of the last dose of investigational product or if both years are the same but the month is after the month of the date of the last dose of investigational product, then the first day of the month will be assigned to the missing day.

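### SAP 18.6 ignores a partial stop date when it checks an imputed start, so some medicines recorded as ended before first dose are counted as concomitant and not as prior

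*SAP*

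**What the plan says.** Five rules act together.

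- **Order (SAP 18.5).** "When the start date and the stop date are both incomplete for a subject, impute the start date first".
- **Year-only start (SAP 18.6.1).** When the recorded year matches that of first dose, "then the day and month of the date of the first dose of investigational product will be assigned to the missing fields". SAP 18.6.2 treats a start with only the month missing in the same way.
- **Check on the imputed start (SAP 18.6).** The rule reads: "If the stop date is complete and the imputed start date is after the stop date, then the start date will be imputed". The value taken is that complete stop. There is no matching check for a partial stop date.
- **Partial stop (SAP 18.7.3 and 18.7).** When the day is missing and, within the same year, "the month is before the month of the date of the last dose of investigational product, then the last day of the month" is assigned. SAP 18.7 then raises a stop that falls too early up to the start: "If the imputed stop date is before the start date (imputed or non-imputed start date), then the imputed stop date will be equal".
- **Classification (SAP 9).** "Prior medication is defined as any medication with a start date prior to the date of the first dose of investigational product". A medicine is concomitant if it starts before first dose and continues after it, or if its start lies from first to last dose inclusive. The second route does not look at the stop date.

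**The concern.** A recorded stop month that lies wholly before the first-dose month is real information: it rules out use on study drug. The check in SAP 18.6 respects that information when the day is recorded and ignores it when the day is missing. Two records that tell the same story can then fall into opposite classes.

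Partial dates are plausible here. Protocol 7.1.1.1 asks for all lifetime psychoactive medicines, and the history will come largely from parents. SAP 9 sets no look-back limit on prior medication and summarises prior and concomitant ADHD medication. At stake is the accuracy of those summaries and listings: an affected record is missing from the prior count and added to the concomitant count.

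**Working it through.** The plan states no figure on this point, so the check is a literal trace of SAP 18.5 to 18.7 and SAP 9. The dates are illustrative assumptions: first dose 12 June 2018, last dose 23 July 2018.

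**Affected record: start 2018, stop March 2018**

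1. Both dates are partial, so the start is imputed first (18.5).
2. The start year equals the first-dose year, so start = 12 June 2018 (18.6.1).
3. The stop date is not complete, so the check in 18.6 is skipped.
4. The stop month is before the last-dose month, so stop = 31 March 2018 (18.7.3).
5. 31 March is before 12 June, so the stop is raised to 12 June 2018 (18.7).
6. The start is not before first dose, so the record is not prior. It lies between first and last dose, so the record is concomitant (SAP 9).

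Step 5 can be removed without changing step 6, because the second route to concomitant status reads only the start. The class is fixed by steps 2 and 3 together with SAP 9.

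**Comparison records, same dosing dates**

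| Recorded start | Recorded stop | Imputed start | Imputed stop | Class |
|---|---|---|---|---|
| 2018 | March 2018 | 12 Jun 2018 | 12 Jun 2018 | concomitant only |
| 2018 | May 2018 | 12 Jun 2018 | 12 Jun 2018 | concomitant only |
| 2018 | 15 March 2018 | 15 Mar 2018 | 15 Mar 2018 | prior only |
| 2017 | March 2018 | 31 Dec 2017 | 31 Mar 2018 | prior only |
| Feb 2018 | March 2018 | 28 Feb 2018 | 31 Mar 2018 | prior only |
| 2018 | June 2018 | 12 Jun 2018 | 30 Jun 2018 | concomitant only |
| 2018 | 2018 | 12 Jun 2018 | 23 Jul 2018 | concomitant only |

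The first two rows are wrong. The last two are truly ambiguous, and concomitant is the cautious choice for them.

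**All month pairings.** With a year-only start in the first-dose year, a first dose in month m allows m − 1 earlier stop months. Summed over the year, 0 + 1 + … + 11 = 66 pairings. All 66 come out concomitant and not prior. The same happens when dosing crosses the year end: start 2017, stop March 2017, first dose 12 December 2017 gives start = stop = 12 December 2017.

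**After extending the check to partial stops.** Start 2018 with stop March 2018 becomes 31 March 2018 for both dates, prior only. With stop May 2018 both become 31 May 2018, prior only. The two ambiguous rows do not change.

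**The case against.** The best defence is that counting uncertain medicines as concomitant is a usual cautious convention, and that only descriptive tables are involved. The second half stands. The first half does not cover these records: a stop month before the first-dose month leaves no uncertainty about on-study use, and SAP 18.6 already accepts that principle for complete dates.

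SAP 9 allows a medicine to be counted in both classes. That does not restore the prior count, because prior status still needs a start before first dose.

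Several stronger readings are tempting, and the documents do not support them.

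- *Every medicine with partial dates that ended before first dose is affected.* No. A complete stop date, a start year before the first-dose year, or a known start month before the first-dose month each gives the right class.
- *The stop-date override in SAP 18.7 causes the error.* It only overwrites the recorded month; the class is the same without it.
- *The tables would suggest prohibited stimulant use on the first day of study drug.* SAP 9 tabulates subjects by preferred term, not by day of use, and under SAP 6 deviations are recorded by the site outside the clinical database and reviewed separately.
- *These are mainly medicines washed out for the study.* Under Protocol 5.2.2 and 7.1.1 a medicine may be stopped for the study only after consent, and planned screening is 28 days. In the example, Visit 0 is 11 June and 28 days earlier is 14 May, so a March stop precedes planned screening. A May stop could be a study washout, but site staff direct those stops, and complete dates are likelier there.
- *Adverse event dates have the same fault.* SAP 18.8 says that incomplete start dates are imputed but gives no algorithm, so no error can be shown.

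**Conclusion.** The concern holds within a narrow scope. Two conditions are needed: a start with the month missing (year-only, or day and year only) in the first-dose year, and a partial stop whose recorded month is before the first-dose month. Every such record is counted as concomitant and left out of prior medication, against its own recorded stop month. No other rule in either document corrects it.

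The trace depends only on the wording of the rules; the dates in it are illustrative. How many records meet both conditions cannot be learned from the documents and is probably small. Any percentage would rest on assumed durations of use and assumed gaps before first dose, so none is offered. The effect is confined to the descriptive prior and concomitant medication summaries and listings, including those for ADHD medication. The efficacy tests, the alpha allocation and the sample size are untouched.

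**What to change.** In SAP 18.6, replace the check with:

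> *If the imputed start date is later than the latest date compatible with the recorded stop date (complete or partial), the start date is set to that latest date.*

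In SAP 18.7, keep the override only for a complete or otherwise non-imputed start date that falls after a partial stop, and query such records. A flat ban on moving the stop outside its recorded month or year would be too broad, because it would leave a complete start of 15 August 2018 with a stop of July 2018 without any rule.

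One detail for the programmer: a start month recorded after the last-dose month, with a year-only stop, can still give an imputed stop before the imputed start. Raising the stop to the start is harmless there. The stop stays in its recorded year, and a medicine started after last dose is neither prior nor concomitant under SAP 9. Such a start can be treated as fixed for the override.

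The cost is one replaced sentence, one narrowed sentence and a small change to the date-derivation program. No analysis or data collection changes.

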18.7.1 Missing Day and Month

- If the year of the incomplete stop date is the same as the year as of the date of the last dose of investigational product, then the day and month of the date of the last dose of investigational product will be assigned to the missing fields
- If the year of the incomplete stop date is before the year of the date of the last dose of investigational product, then 31 December will be assigned to the missing fields
- If the year of the incomplete stop date is after the year of the date of the last dose of investigational product, then 01 January will be assigned to the missing fields.

18.7.2 Missing Month Only

- The day will be treated as missing, and both month and day will be replaced according to the above procedure.

18.7.3 Missing Day Only

- If the month and year of the incomplete stop date are the same as the month and year of the date of the last dose of investigational product, then the day of the date of the last dose of investigational product will be assigned to the missing day.
- If either the year is before the year of the date of the last dose of investigational product or if both years are the same but the month is before the month of the date of the last dose of investigational product, then the last day of the month will be assigned to the missing day.
- If either the year is after the year of the last dose of investigational product or if both years are the same but the month is after the month of the date of the last dose of investigational product, then the first day of the month will be assigned to the missing day.

18.8 Missing Date Information for Adverse Events

For AEs, the default is to only impute incomplete (ie, partially missing) start dates. Incomplete stop dates may also be imputed when calculation of the duration of an AE is required per the protocol. If imputation of an incomplete stop date is required and both the start date and the stop date are incomplete for a subject, impute the start date first.

18.9 Missing Severity Assessment for Adverse Events

If severity is missing for an AE starting prior to the date of the first dose of investigational product, then a severity of “mild” will be assigned. If the severity is missing for an AE starting on or after the date of the first dose of investigational product, then a severity of “severe” will be assigned. The imputed values for severity assessment will be used for incidence summaries, while the actual values will be used in data listings.

18.10 Missing Relationship to Investigation Product for Adverse Events

If the relationship to investigational product is missing for an AE starting on or after the date of the first dose of investigational product, a causality of “related” will be assigned. The imputed values for relationship to double-blind investigational product will be used for incidence summaries, while the actual values will be presented in data listings.

18.11 Character Values of Clinical Laboratory Variables

If the reported value of a clinical laboratory variable cannot be used in a statistical analysis because, for example, a character string is reported for a numerical variable, then the appropriately determined coded value will be used in the statistical analysis. However, the actual values as reported in the database will be presented in data listings.

Table 5: Examples for Coding of Special Character Values for Clinical Laboratory Variables

| Clinical Laboratory Test | Possible Results (in SI units) | Coded Value for Analysis |
|----------------------------|--------------------------------|--------------------------|
| Chemistry: ALT | <5 | 0 |
| Chemistry: AST | <5 | 0 |
| Chemistry: Total Bilirubin | <2 | 0 |
| Urinalysis: Glucose | ≥55 | Positive |
| | ≤0 | Negative |
| Urinalysis: pH | ≥8.0 | 8.0 |

ALT=alanine transaminase; AST=aspartate transaminase

20. APPENDIX

20.1 Appendix 1 Algorithms for Deviation of the Pooled Common Variance

Based on the rationale that the total variance is similar to the within group variance as long as the treatment effect is not too large, a pooled common variance can be estimated by using blinded cumulative primary efficacy data that are collected during the study, up to the time of sample size re-estimation. The pooled common variance can be used along with the pre-specified treatment difference to re-estimate the sample size. Below are steps in detail:

- Ignoring treatment difference and applying the formula below to estimate the pooled sample variance, which is an unbiased estimate of the variance.

$$S_{pooled}^2 = \frac{1}{n_1-1} \sum_{i,j} (X_{ij} - \bar{X})^2,$$

where n_1 is total number of subjects who either completed or discontinued from the study at the time point of the sample size re-estimation. $i = 1, 2$; $j = 1, \dots, n_{1i}$ and $n_1 = n_{11} + n_{12}$.

- Let Δ^* be the alternative hypothesis of treatment mean difference that is pre-specified as 8.4, for which the study is powered. Hence, a common variance that can be used for the sample size re-estimation is:

$$S_{final}^2 = S_{pooled}^2 - \frac{n_1}{4(n_1-1)} \Delta^{*2}.$$

- Applying S_{final}^2 and the assumed true mean treatment effect difference together, an updated effect size can be calculated. Using the effect size, the sample size can be re-estimated ([Friede and Kieser, 2006](#)).

Furthermore, the blinded sample size re-estimation only allow upwards adjustments of the initially (at the study design stage) planned sample size, and using the pooled common variance estimated above to do a blinded sample size-estimation does not inflate the Type I error rate ([Friede and Kieser, 2006](#)).

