### 7.1.2.3 End-of-Study Visit (Visit 6/Early Termination)

All randomized subjects who complete the study or discontinue early will complete Visit 6/early termination (ET).

[Table 1](#) lists the procedures to be completed at Visit 6/ET and should serve as the primary point of reference regarding visit-specific study procedures.

Further clarification on the procedures performed during Visit 6/ET is provided below:

- Unused investigational product and empty containers will be collected to calculate medication compliance.
- After 5 minutes rest, blood pressure and pulse will be collected 3 times (with at least 2 minutes in between each collection) during the visit. The average of each set of 3 measurements will be used to determine continued participation in the study (see [Section 4.4.1](#)).

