2.5 Determination of Sample Size

Approximately 245 subjects will be screened to randomize approximately 195 subjects in a 5:5:5:5:6 ratio to SPD489 5, 10, 20, 30 mg or placebo to achieve 156 completers for the study (30 in each active treatment group and 36 in the placebo group) and 85% power for the primary efficacy analysis at a 2-sided 0.05 significance level.

The sample size planned at study initiation is estimated based on the primary comparison between SPD489 10, 20, 30 mg pooled together (excluding the 5mg) compare with placebo on the primary efficacy endpoint, in a group sequential design with 1 interim analysis using the Lan-DeMets alpha spending function with O'Brien-Fleming boundary for the primary efficacy endpoint. Assumptions for the calculation include the true mean difference of 8.4 with the common standard deviation (SD) of 14 for the primary efficacy endpoint, for an effect size of 0.6, and a dropout rate of 20%.

In order to maintain sufficient study power to detect a clinically meaningful treatment effect for the primary efficacy endpoint, a blinded sample size re-estimation is planned. If the study continues beyond the proposed interim analysis, or if the interim analysis is waived, then the sample size re-estimation will be performed when approximately 75% of the 195 subjects have either completed or discontinued from the study. In this case, cumulative primary efficacy data will be used to estimate a pooled common SD to ensure the variability hypothesized at the design stage is not underestimated. Together with the assumed treatment difference of 8.4, the final total number of subjects to be enrolled will be calculated using the re-estimated pooled SD ([Friede and Kieser 2006](#)). Step by step details for estimating the pooled SD are included in the [Appendix 1](#). Using the pooled common variance estimated to do a blinded sample size re-estimation does not inflate the Type I error.

The final total sample size could potentially be as high as 218 completers, which corresponds to the 97.5% percentile of the distribution of the estimator on the assumed true common SD of 14 postulated at the design stage. If the re-estimated pooled common SD is larger than 14, the sample size will be increased. Otherwise, the sample size will remain the same. Note that the total of 218 completers is not considered a cap. As the final sample size is data driven, a higher number, though unlikely, is possible.

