10.1 Primary Efficacy Endpoint and Analysis

The primary efficacy endpoint is defined as the change from baseline in clinician-administered ADHD-RS-IV Preschool Version Total Score at Visit 6 (Week 6).

The statistical hypotheses of the primary efficacy analysis are:

- The null hypothesis is: there is no treatment difference between pooled SPD489 (10, 20 and 30mg) dose group and placebo at Visit 6 (Week 6)
- The alternate hypothesis is: there is a treatment difference between pooled SPD489 (10, 20 and 30mg) dose group and placebo at Visit 6 (Week 6).

The estimate of primary interest is estimate of the average effect attributable to the experimental treatment (pooled SPD489 10, 20 and 30 mg) as compared to placebo at Visit 6 (Week 6), for all subjects in FAS of the study.

The primary efficacy endpoint will be analyzed using the linear mixed-effects model for repeated measures (MMRM). The analysis includes the fixed categorical effects of treatment, visit, and treatment-by-visit interaction, the covariate of baseline ADHD-RS-IV Preschool Version Total Score, and with the baseline ADHD-RS-IV Preschool Version Total Score-by-visit interaction adjusted in the model. The restricted maximum likelihood method will be used, with an unstructured covariance structure (UN) shared across treatment groups used to model the within-patient errors. The Kenward-Roger method is used to estimate denominator degrees of freedom and adjust standard errors (SEs). The primary contrast of interest will be at Visit 6 (Week 6) for pooled SPD489 (10, 20 and 30mg) dose group compared with placebo.

For the above MMRM analysis, contrast coefficients that are based on the actual sample size of placebo or each dose in the pooled SPD489 group will be used to obtain a weighted average for performing the comparison.

If the UN covariance structure fails to converge, as an alternative, the Toeplitz (TOEP) or Autoregressive (1) [AR(1)] covariance matrix will be applied in that order, that is, test the TOEP structure first, if it does not converge then test the AR(1). Both of these covariance matrices can model data with correlations that decline over time. Comparing AR(1) with TOEP, the AR(1) has less constraining conditions, so when the TOEP structure fails to converge, the AR(1) may still converge. Regardless which covariance structure is chosen, missing data will not be imputed.

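### SAP Appendix 1 corrects the blinded variance as if for two equal groups, and the 218-completer planning figure does not come from the variance used for sizing (minor)

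*SAP*

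**What the plan says.** SAP 20.1 (Appendix 1) sets out the blinded re-estimation in three steps.

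- It computes one pooled variance, S_pooled², over all blinded values. The groups are indexed i = 1, 2, the subjects j = 1 to n_1i, and n1 = n11 + n12. It says that n1 "is total number of subjects who either completed or discontinued from the study at the time point of the sample size re-estimation".
- It subtracts n1/(4(n1−1)) times 8.4² to obtain S_final².
- It uses S_final² with the planned difference to recalculate the sample size, upward only.

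The stated rationale is that the total variance is close to the within-group variance "as long as the treatment effect is not too large".

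SAP 2.5 gives the trigger: "If the re-estimated pooled common SD is larger than 14, the sample size will be increased". It also gives an upper planning figure: the total "could potentially be as high as 218 completers, which corresponds to the 97.5% percentile of the distribution of the estimator" at a true SD of 14. The same figure stands in the protocol synopsis (Number of Subjects) and in protocol 9.5.2. All three places say that it is not a cap. None says whether the estimator is S_pooled or S_final.

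**The concern.** The correction removes the part of the blinded variance that comes from differences between arms. Its size depends on the allocation and on the arm means. A factor of 1/4 is p(1−p) at p = 1/2, and no split in this trial is 1:1. The 5 mg arm is outside the primary comparison, but it cannot be taken out of blinded data. If too much is subtracted, the SD is understated and the added sample is too small; if too little, the reverse.

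The re-estimation is what protects 85% power if the SD exceeds 14, and a statistician has to run it from this text. The figure of 218 is given a precise statistical meaning in three places, so the estimator that sets the sample size should produce it.

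**Working it through.** **Inputs.** Difference 8.4, SD 14, 30 completers per active arm, 36 on placebo, 20% dropout, look at 75% of 195 (SAP 2.5); final nominal level 0.0477 (SAP 2.6.2); candidate curves (SAP 10.4.1). 0.75 × 195 = 146 subjects at the look, and 146 × 0.8 = 117 with a Visit 6 value if dropout is as planned.

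**Base design.** SE = 14 × √(1/90 + 1/36) = 2.761 and 8.4/2.761 = 3.043. Power = Φ(3.043 − 1.980) = 85.6%. The planned 156 completers reproduce as adequate for 85%.

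**Correction term.** As printed: 70.56/4 = 17.64. For 90:36: 90 × 36/126² = 0.204, and 0.204 × 70.56 = 14.40. The difference is 3.24, or 1.65% of 196.

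**Five arms.** V = Σ p_k(m_k − m̄)², with p = 6/26 for placebo and 5/26 for each dose. The arm means come from the SAP curves, scaled (an assumption made here) so that pooled 10–30 mg differs from placebo by 8.4. The expected S_final at a true SD of 14 is √(196 + V − 17.64).

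**Power at a true SD of 16.** S_pooled² is drawn from a noncentral chi-square with n1 − 1 df and noncentrality n1·V/SD². N = max(156, 156 × S_final²/196), and power is the normal formula on 15/26 against 6/26 of N. An SD of 16 needs 156 × 256/196 = 204 completers. With no re-estimation, power would be 75.2%.

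**97.5th percentile at SD 14.** Worked case, 90:36 and n1 = 117: S_pooled² has 97.5th percentile 267.9; less 17.64 × 117/116 = 17.8, this is 250.1; 156 × 250.1/196 = 199 completers.

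Results at n1 = 117:

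| Arm means | V | Expected S_final at SD 14 | Power at SD 16, factor 1/4 | Power at SD 16, factor 0.204 | 97.5th percentile, S_final (1/4) | 97.5th percentile, S_pooled |
|---|---|---|---|---|---|---|
| 90:36 only | 14.40 | 13.88 | 84.6% | 85.0% | 199 | 213 |
| Emax | 14.01 | 13.87 | 84.5% | 85.0% | 199 | 213 |
| Logistic, centre 10 | 18.43 | 14.03 | 85.1% | 85.5% | 203 | 217 |
| Linear | 20.78 | 14.11 | 85.4% | 85.8% | 205 | 220 |
| Logistic, centre 15 | 26.24 | 14.30 | 86.1% | 86.5% | 211 | 225 |

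At n1 = 146, S_final gives 194 to 206.

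**What 218 implies.** 218/156 = 1.397, so S² = 273.9 and SD = 16.55. S_final with the 1/4 term reaches this 97.5th percentile on 90:36 only at n1 of about 61. At n1 = 117 the chance that S_final asks for more than 218 is 0.4% (90:36) to 1.3% (logistic, centre 15), not 2.5%.

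**Alternative constant.** Subtracting the average V of the four curves, 19.9, lowers the worst case at SD 16 to 84.2%, below the 84.5% of the present formula.

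**The case against.** Appendix 1 openly offers an approximation. The printed 17.64 lies inside the five-arm range of 14.0 to 26.2, so over the SAP's own curves the error has no fixed sign. That stands, and it is why the point is minor. Scaling the curves to 8.4 is also a choice made here: as printed they imply pooled differences of 8.0 to 10.6, and the expected S_final² is then 0.6% to 6.0% above 196.

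On 218, SAP 2.5 does not name the estimator, and Appendix 1 uses the word pooled for its first variance. A reader might infer that 218 is an arithmetic error. The documents do not support that: it falls within the 213 to 225 that S_pooled gives at n1 = 117. What stands is the mismatch with S_final, the variance used for sizing.

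Two other stronger readings are tempting.

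- Because n1 counts discontinued subjects and SAP 10.1 says "Regardless which covariance structure is chosen, missing data will not be imputed", a reader might infer that subjects without a value enter the divisor and shrink the SD. The printed indexing matches sum and divisor, and protocol 7.1.2.3 plans a Visit 6/ET assessment for everyone who discontinues. Only a clarification is needed.
- Appendix 1 says of S_pooled² "which is an unbiased estimate of the variance", one step before it subtracts a term. A reader might call this a contradiction. The sentence opens by setting the treatment difference aside, and under that condition the statement is true. It is loose wording, not an error.

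**Conclusion.** Minor. The correction term does not match the allocation, and the stated upper sample size is not what the sizing rule produces. As ordinarily read, the formula leaves power within about 1 point of 85% (84.5% to 86.1% at a true SD of 16, n1 = 117). The initial 156 completers and the upward-only rule are unaffected, and no decision depends on 218.

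This rests on 20% of subjects lacking a Visit 6 value at the look, on the SAP curves scaled to 8.4, and on sum and divisor covering the same subjects. How 218 was derived is not shown, so a different estimator is the likely explanation, not an established one.

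No single constant fits every dose-response shape. If all four doses, 5 mg included, had the full effect, V would be (6/26)(20/26) × 70.56 = 12.53. With the present term, power evaluated at the expected variance would then be 84.2% to 84.4% for true SDs of 15 to 18.

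**What to change.** In SAP Appendix 1:

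- Replace the factor 1/4 by the planned allocation product for the primary comparison, 90 × 36/126² = 0.204, so that the term is n1/(n1−1) × 14.4. At SD 16 this holds power at about 85.0% or above under all four SAP curves. The cost is 156 × 3.24/196 = 2.6 more completers when an increase is triggered. Do not use an average five-arm value of 19.9.
- State that n1 is the number of subjects with an observed Visit 6 change from baseline, so that sum and divisor match.

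In SAP 2.5, the protocol synopsis and protocol 9.5.2:

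- Name S_final as the re-estimated SD.
- Restate 218 as the 97.5th percentile of that estimator, showing the n1 and correction term assumed (about 202 at n1 = 117 on 90:36 with the 0.204 term). Keep it as a planning figure and not a cap.

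The cost is wording in one appendix and one figure in three places, made before the blinded look.
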